12.4 Character Values of Clinical Laboratory Evaluation

If any of the measurements of the clinical laboratory results are collected including a sign of inequality, replace it as the following to summarize. When presenting a list by subject, present the recorded values in the CRF.

- ➤ If recorded as equal or above (i.e., >=100 or >100), replace with minimum value (i.e., 100)
- ➤ If recorded as equal or below (i.e., <=4 or <4), replace with maximum value (i.e., 4)

13. INTERIM ANALYSIS

An interim analysis was not planned in this study.

14. CHANGE FROM PROTOCOL

Categor	Protocol	Statistical Analysis Plan	Reasons for
Determination of gallstones	The diagnosis of gallstone formation is based primarily on the results of abdominal ultrasound and is supplemented by abdominal CT scan results. If the results of the two tests differ, abdominal ultrasound result should be considered first for gallbladder gallstones, and both abdominal ultrasound and abdominal CT should be considered in the case of bile duct gallstones or intrahepatic bile duct gallstones.	The diagnosis of gallstone formation is based primarily on the results of abdominal ultrasound and is supplemented by abdominal CT scan results. If the results of the two tests differ,	Additional techniques for cases in which only abdominal CT scan results

Protocol No.: DW_UDCA005 English Translation Version

15. SAS PROCEDURE FOR TESTING

15.1 Normality Test

PROC UNIVARIATE DATA=dataset NORMAL;
VAR variable;
RUN;

15.2 Testing for Within-Groups

Paired t-test or Wilcoxon signed-rank test

PROC UNIVARIATE DATA=dataset;

VAR diff;

RUN;

McNemar's Test

PROC FREQ DATA=dataset;

TABLE treatment* variable/AGREE;

RUN;

15.3 Comparison for Between Treatment Groups

ANOVA

PROC GLM DATA = dataset;

CLASS treatment;

MODEL variable = treatment;

RUN;

Kruskal-Waillis test

PROC NPAR1WAY DATA = dataset WILCOXON;

CLASS treatment;

VAR variable;

RUN;

Chi-square or Fisher's exact test

PROC FREQ DATA = dataset;

TABLE treatment * variable/CHISQ FISHER;

RUN;

ANCOVA

PROC GLM DATA = dataset;

CLASS treatment covariate (categorical);

MODEL variable = treatment covariate;

LSMEANS treatment/PDIFF CL STDERR;

ESTIMATE 'DWJ1319 600 mg or 300 mg vs Placebo' treatment 1 -1;

RUN;

Logistic regression model

PROC LOGISTIC DATA = dataset;

CLASS treatment covariate (categorical)/param=ref ref=last;

MODEL variable = treatment covariate;

Protocol No.: DW_UDCA005 English Translation Version

ESTIMATE 'DWJ1319 600 mg or 300 mg vs Placebo' treatment 1 -1 /EXP;

RUN;

Logistic regression model (in case of including cells with frequency of 0)

PROC LOGISTIC DATA = dataset;

CLASS treatment covariate (categorical)/param=ref ref=last;

MODEL variable = treatment covariate/ firth clodds=pl;

RUN;

Cox Proportional Hazards regression Model

PROC PHREG DATA = dataset;

CLASS treatment covariate (categorical)/param=ref ref=last;

MODEL time * status(censored) = treatment covariate / RL;

CONTRAST 'DWJ1319 600 mg or 300 mg vs Placebo' treatment 1 -1 / ESTIMATE =EXP;

RUN;

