8.4.1 Primary Efficacy Analysis

The primary efficacy endpoint is the percentage of subjects with gallstone formation within 12 months of gastrectomy based on the external investigator's assessment.

For the superiority test of DWJ1319 over placebo on the incidence of gallstone formation, sequential multiple testing will be performed for each treatment group according to the fixed sequence method.

Step 1: Superiority testing for DWJ1319 600 mg compared with placebo (5% significance level)

Protocol No.: DW_UDCA005 English Translation Version

Step 2: Superiority testing for DWJ1319 300 mg compared with placebo (5% significance level)

As DWJ1319 600 mg is expected to be relatively more effective in preventing gallstones compared to DWJ1319 300 mg, the efficacy assessment of DWJ1319 600 mg versus placebo is given priority.

The step 2 test can be performed only if the result of the step 1 test is statistically significant, and conclusions about the superiority of DWJ1319 over placebo will be drawn based on the test result from each step. If the result of the step 1 test is not statistically significant, the step 2 test will not be performed, and it will be concluded that both treatment groups of DWJ1319 have failed to demonstrate superiority over placebo.

The frequency, percentage (%), and corresponding 95% confidence intervals are presented for the subjects with gallstone formation within 12 months by each treatment group. The comparison between each treatment group of DWJ1319 versus the placebo is analyzed using the Logistic Regression Model, with the lymph node resection range (D1+, D2) and the type of gastrectomy (Total gastrectomy, partial gastrectomy) as the covariates and the respective factors are defined as the following. The factors are defined as treatment group (DWJ1319 600 mg vs Placebo) for Step 1, treatment group (DWJ1319 300 mg vs Placebo) for Step 2, and treatment group (Placebo, DWJ1319 600 mg and DWJ1319 300 mg) for sensitivity analysis. Logistic Regression Model results are presented as odds ratios, corresponding 95% confidence intervals and two-sided p-values, and p-value is used for the final determination.

A summary of the data is presented in the following tables.

- T. Percentage of Subjects with Gallstone Formation within 12 month by the External Investigator's Assessment [DWJ1319 600mg vs Placebo] (FAS)

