8.4.2 Secondary Efficacy Analysis

1) Percentage of subjects forming gallstones within 3, 6, 9, and 12 months from

Protocol No.: DW UDCA005

English Translation Version

gastrectomy

- 2) Percentage of subjects forming gallstones within 3, 6, and 9 months from gastrectomy as assessed by the external investigator
- 3) Percentage of subjects forming biliary sludge within 3, 6, 9, and 12 months from gastrectomy

For the secondary endpoints 1), 2), and 3), the comparison between each treatment group of DWJ1319 versus the placebo is analyzed using the Logistic Regression Model, with the treatment groups (DWJ1319 600 mg/DWJ1319 300 mg vs Placebo) as the factor and the lymph node resection range (D1+, D2) and the type of gastrectomy (Total gastrectomy, partial gastrectomy) as the covariates. Logistic Regression Model results are presented as odds ratios, corresponding 95% confidence intervals and two-sided p-values.

4) Time to gallstone formation

For the time to gallstone formation, the median and corresponding 95% confidence intervals, and standard error values are presented. The comparison between each treatment group of DWJ1319 versus the placebo is analyzed using the Cox Proportional Hazards regression Model and the two-sided p-values are presented, with the treatment groups (DWJ1319 600 mg/DWJ1319 300 mg vs Placebo) as the factor and the lymph node resection range (D1+, D2) and the type of gastrectomy (Total gastrectomy, partial gastrectomy) as the covariates.

A summary of the data is presented in the following tables.

- T. Percentage of Subjects with Gallstone Formation within 3, 6, 9, 12 month by the Investigator's Assessment (FAS)
- T. Percentage of Subjects with Gallstone Formation within 3, 6, 9, 12 month by the Investigator's Assessment (PPS)
- T. Percentage of Subjects with Gallstone Formation within 3, 6, 9 month by the External Investigator's Assessment (FAS)
- T. Percentage of Subjects with Gallstone Formation within 3, 6, 9month by the External Investigator's Assessment (PPS)
- T. Percentage of Subjects with Biliary Sludge Formation within 3, 6, 9, 12 month by the Investigator's Assessment (FAS)
- T. Percentage of Subjects with Biliary Sludge Formation within 3, 6, 9, 12 month by the Investigator's Assessment (PPS)
- T. Time to Gallstone Formation (FAS)
- T. Time to Gallstone Formation (PPS)

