9.2.4 Evaluation of Each Laboratory Parameter

For the continuous variables of the clinical laboratory test categories, descriptive statistics (number of subjects, mean, standard deviation, median, minimum, and maximum values) are presented for each treatment group with respect to the measured value and the change relative to the baseline at each visit. For intra-group changes relative to the baseline, paired t-test or Wilcoxon signed rank test is performed for comparison according to the result of the normality test. For the differences among the treatment groups, ANOVA or Kruskal-Wallis test is performed for comparison according to the result of the normality test.

A summary of the data is presented in the following tables.

- T. Summary of Hematology Data [Parameter] (Safety Set)
- T. Summary of Serum Chemistry Data [Parameter] (Safety Set)
- T. Summary of Urinalysis Data [Parameter] (Safety Set)

In order to confirm any changes in normality status after the administration of the investigational product compared to the baseline, data is divided into the normal, abnormal NCS and abnormal CS categories and summarized in shift table form by treatment group at each evaluation point. The McNemar's test is used for intra-group changes and the chi-square test or the Fisher's exact test is used to compare differences among the treatment groups. In addition, a list is presented of subjects who were normal or abnormal NCS at baseline but showed abnormal CS changes after administration of the investigational product.

A summary of the data is presented in the following table and list.

- T. Shift from Baseline at Post-Baseline on Hematology Data [Parameter] (Safety Set)
- T. Shift from Baseline at Post-Baseline on Serum Chemistry Data [Parameter] (Safety Set)
- T. Shift from Baseline at Post-Baseline on Urinalysis Data [Parameter] (Safety Set)
- L. Subjects Shifting from Normal or NCS at Baseline to CS at Post-Treatment on Laboratory (Safety Set)

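### SAP 15: the contrast labelled as dose versus placebo gives a different comparison in a three-arm logistic or Cox model, and the McNemar code does not test change from baseline

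*Protocol*

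**What the plan says.** **Model code (SAP 15.3).** The logistic and Cox templates both set "CLASS treatment covariate (categorical)/param=ref ref=last". The logistic template then requests "ESTIMATE 'DWJ1319 600 mg or 300 mg vs Placebo' treatment 1 -1 /EXP", and the Cox template requests "CONTRAST 'DWJ1319 600 mg or 300 mg vs Placebo' treatment 1 -1 / ESTIMATE =EXP". The ANCOVA template has an ESTIMATE line with the same label and the same two coefficients, under PROC GLM's own coding. The Firth template for zero cells has no such line.

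**Which models these serve.** For the confirmatory tests, SAP 8.4.1 uses two-level factors: "The factors are defined as treatment group (DWJ1319 600 mg vs Placebo) for Step 1", and likewise 300 mg against placebo for Step 2. It then adds a three-level model, with "treatment group (Placebo, DWJ1319 600 mg and DWJ1319 300 mg) for sensitivity analysis". For the secondary logistic and Cox models, SAP 8.4.2 describes the analysis "with the treatment groups (DWJ1319 600 mg/DWJ1319 300 mg vs Placebo) as the factor". It does not say whether one three-arm model or two two-arm models are fitted. SAP 8.4.3 words the ANCOVA and the exploratory logistic models the same way.

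**Within-group code (SAP 15.2).** The McNemar template is "TABLE treatment* variable/AGREE". SAP 9.2.4 assigns McNemar's test to changes within a treatment group relative to baseline, where "data is divided into the normal, abnormal NCS and abnormal CS categories and summarized in shift table form".

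**The concern.** With reference coding, a three-level treatment has two coefficients, each a level minus the reference. Weighting them 1 and -1 cancels the reference. The output is then not a comparison of both doses with placebo, whatever its label says. A programmer following the template in the three-arm sensitivity model could print a dose-versus-dose odds ratio as a result against placebo. That table is meant to support the primary finding.

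The McNemar template has a different fault. A within-group change needs each subject's baseline category crossed with the same subject's post-dose category. A table of treatment by result holds no paired data, so a symmetry test on it has no meaning as a test of change.

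**Working it through.** **Inputs.** SAP 4.6 gives a placebo rate of 18%, an active rate of 7% for both doses, two-sided 5%, 80% power and 1:1:1 allocation. The Study 1 rates in the same section are 13.21% (300 mg) and 1.64% (600 mg). Coding and contrasts are those of SAP 15.3.

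**The plan's own figure.** (1.96 + 0.842)² × (0.07×0.93 + 0.18×0.82) / 0.11² = 7.851 × 0.2127 / 0.0121 = 138.01, which matches the stated 138 per group. Then 138/0.8 = 172.5, rounded up to 173, and 3 × 173 = 519. The checks below use 138 per arm and no covariates.

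**Intended comparison.** The odds are 0.07/0.93 = 0.0753 and 0.18/0.82 = 0.2195, so the odds ratio of each dose against placebo is 0.343. The variance of its log is 1/(138×0.07×0.93) + 1/(138×0.18×0.82) = 0.1113 + 0.0491 = 0.1604, so the standard error is 0.4005 and z = -1.070/0.4005 = -2.67.

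**What the coded line returns on three arms.** Let b1 and b2 be the log odds ratios of the first and second level against the last. The line estimates b1 - b2, which is first level against second. The table covers all six level orders. The last column keeps 18% for placebo and uses the Study 1 dose rates, as illustration only.

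| Level order | Comparison returned | 18% / 7% / 7% | Study 1 dose rates |
|---|---|---|---|
| 300, 600, placebo | 300 vs 600 | 1.00 | 9.13 |
| 600, 300, placebo | 600 vs 300 | 1.00 | 0.110 |
| placebo, 300, 600 | placebo vs 300 | 2.92 | 1.44 |
| placebo, 600, 300 | placebo vs 600 | 2.92 | 13.2 |
| 300, placebo, 600 | 300 vs placebo | 0.343 | 0.693 |
| 600, placebo, 300 | 600 vs placebo | 0.343 | 0.076 |

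For example, (0.1321/0.8679)/(0.0164/0.9836) = 9.13. No order gives both dose-versus-placebo results. In 20,000 simulated trials at 18%/7%/7% with placebo last (unadjusted Wald test), the coded line was significant in about 4% of trials. The contrasts (1 0) and (0 1) were significant in about 79%.

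**Two arms.** There is one treatment coefficient. With placebo as reference, the weight 1 on it gives the intended 0.343, and the -1 has no parameter to act on.

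**ANCOVA.** PROC GLM carries one parameter per level, so 1 and -1 is correct for two levels with placebo last. With three levels it compares only the first two.

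**McNemar code.** Take two arms with identical results, 130 not clinically significant and 8 clinically significant in each. The treatment-by-result table has off-diagonal cells 8 and 130, so the statistic is (8 - 130)²/138 = 107.9, p about 3e-25. Now take three identical arms with 100 normal, 30 NCS and 8 CS in each. The symmetry statistic is 70²/130 + 92²/108 + 22²/38 = 37.7 + 78.4 + 12.7 = 128.8 on 3 df, p about 1e-27. These counts are illustrative. They show that the coded test gives extreme p-values when the arms do not differ and no baseline value has entered the table.

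**The case against.** The best defence is that SAP 15 is placeholder code, and that its label, naming one dose or the other, describes a single line reused on a two-level factor. SAP 8.4.1 defines exactly such factors for Steps 1 and 2. This stands for the confirmatory tests. It does not cover the three-level sensitivity model, for which the SAP offers no other logistic code except the Firth variant for zero cells.

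It is also true that correct comparisons are available beside the faulty line. With placebo last, each reference-coded coefficient is already dose versus placebo; the Cox code requests hazard-ratio limits, and the ANCOVA code requests all pairwise differences. A conflict might therefore be noticed, but the mislabelled line would still be printed.

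A reader might infer several stronger points that the documents do not support:

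- That the primary conclusion or the sample size is at risk. Steps 1 and 2 are two-arm fits and do not depend on the contrast when placebo is the reference.
- That every secondary and ANCOVA result is wrong. This holds only if they are fitted on three arms, which SAP 8.4.2 and 8.4.3 do not state.
- That 1.00 or 9.13 is what the trial would print. The SAP fixes no level order: its arm names sort with placebo last, but SAP 8.4.1 lists placebo first. The 1.00 also relies on the equal 7% assumed for both doses, and the 9.13 on 6-month rates in obese patients.
- That three categories defeat the coded option. AGREE gives Bowker's symmetry test on a larger square table; the fault is which variables are crossed.

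On McNemar, the prose in SAP 9.2.4 correctly describes a shift from baseline by group, and Protocol 14.5.2 plans no within-group test. These are supplementary safety p-values. The code still contradicts the prose.

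**Conclusion.** The point holds in a limited form. Followed as written in the three-arm sensitivity model, SAP 15.3 returns the first against the second non-reference level under a placebo label. That is dose against dose with placebo last (1.00 against an intended 0.343 at the planning rates), and otherwise placebo with one dose only. Secondary and exploratory logistic, Cox and ANCOVA results are exposed only if three arms are fitted together. The McNemar code is wrong under any level order. Severity is minor: sensitivity, secondary, exploratory and supplementary safety output is affected, and the confirmatory tests are not. The figures assume unadjusted models and 138 per arm.

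**What to change.** - State the level order (300 mg, 600 mg, placebo) and name placebo as the explicit reference.
- In PROC LOGISTIC and PROC PHREG, keep reference coding and request one labelled contrast per dose for three-arm fits: `1 0` for 300 mg vs placebo and `0 1` for 600 mg vs placebo. For two-arm fits, use a single `1`. An LSMEANS request is not a substitute here unless GLM coding is used.
- In a three-level PROC GLM, use `1 0 -1` and `0 1 -1`.
- State in SAP 8.4.2 and 8.4.3 whether those models are fitted on two or three arms.
- For shift tables, run PROC FREQ by treatment with `TABLES baseline*post / AGREE`. Report Bowker's symmetry test for the three categories, or McNemar's test after collapsing to CS / not CS.

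The cost is a few code lines in SAP 15 and a clarifying sentence in each of 8.4.2 and 8.4.3. Design, data collection and sample size do not change.

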Appendix. LIST OF TABLES, FIGURES AND LISTINGS

- 1. Mock-Up Tables
- 2. Mock-Up Figures
- 3. Mock-Up Listings
